## General Study Schedule

### To obtained informed consent

Day 1	Screening  1) Informed Consent, HIPAA authorization 2) OSDI and CLDEQ-8  3) Assessment of TBUT
Days 1-8 (1 week)	Wash-out period
Days 9	Baseline Testing (1) OSDI, CLDEQ-8, additional questions (skip questions 3 and 5) (2) Battery of Clinical tests (3) Randomization of lenses
Days 9-39 (30 days)	Test Period 1 Wear of treated or untreated CL
Day 40	Post CL Wear Testing (1) OSDI, CLDEQ-8, additional questions (2) Battery of Clinical Tests
Day 40-47 (1 week)	1 week Wash-out Period
Days 48-78 (30 days)	Test Period 2 Wear of treated or untreated CL
Day 79	Post CL Wear Testing (1) OSDI, CLDEQ-8, additional questions (2) Battery of Clinical Tests

### Data Collection:

Data will be kept primarily electronically through REDCap, a secure database application designed to support data capture for research studies. The data will be collected on encrypted and password protected electronic devices. An electronic and hard copy versions of the OSDI and CLDEQ-8 will be available. The hard copy of the questionnaires will be used only if the secure web link or server is not functioning. As soon as the server is functioning, the data from the paper survey will be uploaded to REDCap. The battery of clinical tests will be completed on a form which will be uploaded to REDCap. All data will be de-identified other than by code. The study data will be reviewed by Tangible Science, LLC, and members of this study team only.

## Statistical Analysis

The key values used for analysis in this study will be differences in CLD and DE symptoms following scleral lens wear with Tangible Hydra-Peg and that found after untreated scleral lens wear. In addition, we will examine differences in CLD and DE signs between Tangible Hydra-Peg scleral lens wear and untreated scleral lens wear. Preliminary data analyses will include inspection for kurtosis and skewness of each distribution and test for normality, using the Shapiro-Wilk test. Normal distributions will be analyzed using a paired t-test. Non-normal distributions will be analyzed with the Wilcoxon Signed Ranked test.

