**Abstract:**

Dry eye (DE) is a common complaint of millions of people worldwide with a significant impact on quality of life. For decades, this condition has presented a challenge to eye care professionals as conventional therapies are often ineffective. Recently, scleral lenses have demonstrated to be a promising therapeutic and vision rehabilitative option for dry eye sufferers. Nonetheless, despite the benefits of scleral lenses for dry eye patients, inadequate wettability of scleral lenses with subsequent diminished comfort and visual clarity remains a concern for scleral lens wearers with dry eye.

Tangible Hydra-PEG™ (Tangible Science LLC, Menlo Park, CA, USA) is a novel coating technology designed to improve lens wettability, deposit resistance and tear film breakup time, ultimately enhancing contact lens comfort. While studies have shown that Tangible Hydra-Peg technology can improve contact lens discomfort (CLD) in soft contact lens and gas permeable lens wearers, to our knowledge, no clinical research investigation has examined the benefits of this new coating on scleral lens wear in dry eye sufferers. As such, the aim of this study is to compare the CLD and DE symptoms of dry eye scleral lens wearers between Tangible Hydra-Peg treated scleral lens wear and untreated scleral lens wear. CLD and DE signs will also be assessed to corroborate our findings.

This will be the first randomized double masked cross-over study to examine CLD and DE symptoms of Tangible Hydra-Peg treated scleral lens wear as compared to untreated scleral lens wear in the dry eye patient population. Tangible Hydra-Peg treated scleral lenses can potentially minimize CLD and DE symptoms, ultimately improving outcomes for patients coping with dry eye disease. This study will provide new information about this innovative technology and help practitioners envisage rehabilitative options which will best optimize the quality of life of this important patient population.

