## **Specific Aims:**

1. The primary goal of this study is to compare the CLD and DE symptoms of moderate to severe DE subjects between 30 days of Tangible Hydra-Peg treated scleral lens wear and 30 days of untreated scleral lens wear.  
Hypothesis: CLD and DE symptoms will be significantly better after 30 days of Hydra-Peg treated scleral lens wear as compared to 30 days of untreated scleral lens wear.
2. The secondary goal of this study is compare the CLD and DE signs of moderate to severe DE subjects between 30 days of Tangible Hydra-Peg treated scleral lens wear and 30 days of untreated scleral lens wear in DE subjects. As DE can impact vision quality and Hydra-Peg may impact contact lens wearing times, as a subanalysis, we will also examine contact lens wearing times and quality of vision such as frequency of foggy vision between treated and untreated scleral lens wear.

Hypothesis: CLD and DE signs will be significantly better after 30 days of Hydra-Peg treated scleral lens wear as compared to 30 days of untreated scleral lens wear. Frequency of foggy vision and contact lens wearing time will be significantly better after 30 days of Hydra-Peg treated scleral lens wear as compared to 30 days of untreated scleral lens wear.

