## **Methods:**

### Participant Recruitment

In a multi-center randomized double-masked cross-over study, 30 scleral lens wearers with CLD and moderate to severe DE shall be recruited for a non-significant risk 1-month study. Participants will be enrolled at three geographically diverse academic site locations across North America (Fort Lauderdale, FL, Chicago, Illinois, and Sacramento, CA). The participants will be randomly selected from those exhibiting CLD and moderate to severe symptomatic dryness as determined by the validated and commonly used Ocular Surface Disease Index (OSDI) dry eye questionnaire (Appendix A) and the validated Contact Lens Dry Eye Questionnaire-8 (CLDEQ-8) (Appendix B). These symptom surveys are recommended to be included in a clinical study assessing DE and CLD by expert researchers of the International Dry Eye Workshop and the International Workshop on Contact Lens Discomfort respectively. The participants will be 18 to 70 years of age and have the presence of reduced tear film break up time (TBUT), a sign of DE and CLD.

A participant will be defined as a scleral lens wearer if he or she reports wearing his or her lenses at least 8 hours per day for at least 5 days per week and have had their habitual lenses no longer than 1 year. Due to the widely varying parameters of scleral lenses and lens diameter having an impact on comfort, in this study scleral lens wear will be defined as 15.0 mm to 19.00 mm inclusive. All participants will be required to remain in primarily the same scleral lens

parameters including material throughout the study, except for the change in lens coating. Except for the wash-out periods, all subjects will be required to continue with the same supportive dry eye therapy and use hydrogen peroxide for lens care throughout the study.

Participants with the following will be excluded from this study: disorders that affect sensitivity (herpetic disease, severe diabetes mellitus), anatomic variations of the conjunctiva that can impair proper scleral lens fitting, pregnancy, and significant visual impairment that could confound the results of the study which, for the purposes of this study, will be defined as best corrected Snellen visual acuity worse than 20/30 in either eye or any other ocular pathology (e.g. glaucoma, macular degeneration, keratoconus) other than DE, which may significantly impact visual function.

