### Experimental Design

30 subjects with symptomatic moderate to severe dry eye and symptoms of CLD will complete a double-masked cross-over study. The participants will be randomly chosen to wear their habitual untreated scleral lenses or Hydra-Peg treated scleral lenses first for 30 days. Half of the participants (15) will be randomly chosen to wear the Hydra-Peg treated scleral lenses first for 30 days, and the other half of the participants (15) will be chosen to wear their habitual untreated scleral lenses for 30 days first. One week wash-out periods with no lens wear will be placed before and between the 30-day test periods. The OSDI, CLDEQ-8, a battery of dry eye diagnostic tests, and tests which will assess the impact of contact lenses on the ocular surface will be administered from 3:00 to 5:00 pm at baseline, after the first test period, and after the cross-over. Contact lens wearing time and questions related to quality of vision will also be collected at baseline, after the first test period, and after the cross-over.

The battery of clinical dry eye sensitive tests will include, TBUT of the ocular surface, and ocular surface staining. TBUT over the surface of the scleral lenses, lid wiper epitheliopathy (LWE), and contact lens-related papillary conjunctivitis we will also be examined as they these factors may change with alteration of a contact lens surface.

The study will be double-masked. Lens pairs will be supplied in identical cases, differing only by code mark unknown to the tester. Only one lens pair during the respective test period (treated or untreated) will be given to each participant. The general study schedule following recruitment is described below.

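### Does the lack of a both-or-either rule for the two symptom questionnaires inflate the false-positive rate of the primary claim?

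*Combined protocol and SAP*

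**What the plan says.** Specific Aims sets one primary goal covering two kinds of symptom, with the hypothesis that "CLD and DE symptoms will be significantly better after 30 days of Hydra-Peg treated scleral lens wear as compared to 30 days of untreated" wear. The Abstract pairs them in the same way: "the aim of this study is to compare the CLD and DE symptoms of dry eye scleral lens wearers".

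Participant Recruitment names the two questionnaires, OSDI and CLDEQ-8, and uses them for eligibility. Experimental Design and the General Study Schedule make them outcomes, given at baseline and after each 30-day period. No section labels either one a primary endpoint. That there are two primary scales is an inference, though a safe one, from the primary goal and the only two symptom questionnaires named.

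The Statistical Analysis section repeats the pairing ("The key values used for analysis in this study will be differences in CLD and DE symptoms following scleral lens wear with Tangible Hydra-Peg") and specifies the tests: "Normal distributions will be analyzed using a paired t-test. Non-normal distributions will be analyzed with the Wilcoxon Signed Ranked test". It gives no alpha, sidedness, ranking of the scales or multiplicity rule, and no other section supplies them.

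**The concern.** Two tests serve one primary aim, and the section where a decision rule belongs has none. If either scale could carry the claim, there would be two chances of a false positive with no adjustment.

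The more practical worry is a split result, with one scale significant and the other not. The same data would be a primary success under one reading and a failure under the other, and the reading could be chosen after the results are known. If the coating truly helped only one scale, and that scale had 80% power, an either-scale rule would declare the primary hypothesis met in about 80% of trials; a both-scales rule would do so in 2.0% to 2.5%.

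**Working it through.** The plan states no alpha, power or sample-size derivation, so it has no figure of its own to reproduce.

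**Inputs**
- From the document: two scales; paired tests; 30 subjects in a cross-over (Experimental Design); a directional hypothesis joined by and (Specific Aims).
- Assumed: two-sided 0.05 per test, which is 0.025 in the direction of benefit (critical value 1.96); correlation r between the two treatment differences from 0 to 0.9.

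**Step 1: both scales required.** The chance that two events both occur cannot exceed the chance of either one. If at least one scale has no true effect, then

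P(both show benefit) ≤ P(the null scale shows benefit) = 0.025.

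This holds for every correlation and for any true effect on the other scale.

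**Step 2: no true effect on either scale.**

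P(both) = P(Z1 > 1.96, Z2 > 1.96), from the bivariate normal with correlation r.

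P(either) = 0.025 + 0.025 − P(both).

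At r = 0: P(both) = 0.025² = 0.000625, and P(either) = 0.05 − 0.000625 = 0.0494.

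| r | Both show benefit | At least one shows benefit |
|---|---|---|
| 0 | 0.06% | 4.94% |
| 0.3 | 0.24% | 4.76% |
| 0.5 | 0.46% | 4.54% |
| 0.7 | 0.83% | 4.17% |
| 0.9 | 1.48% | 3.52% |

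Simulated paired t-tests with n = 30 (400,000 replicates) agree. At r = 0, 0.5 and 0.9 they give 4.87%, 4.58% and 3.55% for at least one scale, and 0.06%, 0.44% and 1.46% for both. Counting significance in either direction, the at-least-one rate runs from 9.75% (r = 0) to 7.04% (r = 0.9).

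**Step 3: which column applies.** Specific Aims, the Abstract and Statistical Analysis all link CLD symptoms and DE symptoms with and. None says or, either, or at least one. The middle column, with the 2.5% ceiling from Step 1, is therefore the one that fits the text.

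**Step 4: what each rule does to power.** Suppose, for illustration, 80% power on each scale alone.
- r = 0: both = 0.8² = 0.64; at least one = 1.6 − 0.64 = 0.96; exactly one = 0.96 − 0.64 = 0.32.
- r = 0.9: both = 0.75; at least one = 1.6 − 0.75 = 0.85; exactly one = 0.85 − 0.75 = 0.10.

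Holm's procedure gives power for at least one scale of about 91% to 77% over the same range, with a false claim of benefit at or below about 2.5%. Each rule gives up something, and none is better on all counts.

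**The case for a change.** The strongest contrary argument is that a hypothesis is not a decision rule. The word and in Specific Aims shows what the sponsor expects. It does not bind the analyst, and the section that should bind is silent. Split results would not be rare: about 32% to 10% of trials at 80% power per scale, and about 50% to 15% at 50% power (r = 0 to 0.9). Writing the rule down would take two sentences.

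Part of this stands. The level and sidedness are absent, and the success rule has to be read from the hypothesis. But the split-result figures rest on assumed power and on a correlation the document does not give. Their upper ends need r = 0, an unlikely extreme for two symptom questionnaires that the same person completes at the same visit. When a split result does occur, the hypothesis as worded is not met, and each scale can still be reported separately. A claim of primary success on one scale would be a visible departure from Specific Aims.

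Writing the rule down would also not settle which rule is best. With 80% power per scale at n = 30 (an effect of 0.53 SD of the paired difference, assumed), restoring 80% for both would take about 39 to 34 completers. Holm, or ranking one scale first, avoids that cost but changes the claim being made. Reasonable statisticians differ on this choice.

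**Conclusion.** The omission is real, but no change follows from it. Followed as written, the primary hypothesis needs both scales, and a false claim that it is met occurs in at most 2.5% of trials at an assumed two-sided 0.05 (0.06% to 1.48% if neither scale has a true effect). No multiplicity adjustment is needed. The 4.9% to 3.5% range belongs to an either-scale rule found nowhere in the document, and even that stays below 5% in the direction of benefit.

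What is missing is a conventional level and a restatement of what the hypothesis already implies. An analyst would supply both without difficulty. The plan makes no power statement, so the lower power of a both-scales rule contradicts nothing in it.

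The conclusion rests on reading and literally, on the assumed 0.05 level, and on each test being valid by itself. Any effect of choosing the test after Shapiro-Wilk, or of period differences, lies outside these figures.

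### Does leaving open which eye, or what two-eye summary, supplies each secondary sign undermine the sign comparisons?

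*Combined protocol and SAP*

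**What the plan says.** All references are to the combined protocol and SAP.

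- **Design.** Experimental Design states that "30 subjects with symptomatic moderate to severe dry eye and symptoms of CLD will complete a double-masked cross-over study". Treatment is given by pair: "Only one lens pair during the respective test period (treated or untreated) will be given to each participant". Both eyes of a participant therefore have the same coating status in each period.
- **Signs.** The same section lists five. Two come from "The battery of clinical dry eye sensitive tests will include, TBUT of the ocular surface, and ocular surface staining". The other three are "TBUT over the surface of the scleral lenses, lid wiper epitheliopathy (LWE), and contact lens-related papillary conjunctivitis".
- **Aim.** Specific Aims puts the signs under the secondary goal, with a directional hypothesis: "CLD and DE signs will be significantly better after 30 days of Hydra-Peg treated scleral lens wear".
- **Analysis.** Statistical Analysis says "In addition, we will examine differences in CLD and DE signs between Tangible Hydra-Peg scleral lens wear and untreated scleral lens wear". Normal distributions go to a paired t-test and others to the Wilcoxon signed-rank test. No eye or two-eye summary is named.
- **Eye wording elsewhere.** Participant Recruitment excludes people with "best corrected Snellen visual acuity worse than 20/30 in either eye", which is an eligibility rule. The tear break-up criterion, that participants "have the presence of reduced tear film break up time (TBUT), a sign of DE and CLD", names no eye.
- **Recording.** Data Collection says the clinical tests go on a form uploaded to REDCap. It does not say whether each sign is recorded in one eye or both.

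**The concern.** All five signs can be measured in each eye, both eyes are treated alike, and the plan expects a significant result for them. If both eyes are recorded, at least three participant-level values are available per sign: right eye, left eye and the mean of the two. Worse eye and a randomly chosen eye are open as well. An analyst who tried several and reported the most favourable would exceed the nominal error rate. An analyst who entered both eyes as separate rows would treat 60 correlated observations as independent, which neither named test allows for.

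At stake is the credibility of the Aim 2 sign results. The OSDI, the CLDEQ-8 and wearing time give one value per participant, so the symptom comparison in Aim 1 is not touched.

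**Working it through.** The plan states no significance level, effect size, SD or between-eye correlation, so it has no figure of its own to reproduce. The check asks how much each way of filling the gap would matter.

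**Inputs.** From the documents: 30 participants in a cross-over, lenses worn in pairs, five signs. Assumed: two-sided 5%, bivariate normal treated-minus-untreated differences with equal SD in the two eyes, no true effect, and a between-eye correlation of those differences, ρ, of 0, 0.3, 0.5, 0.7 or 0.8.

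**Step 1. A fixed choice is valid.** With one value per participant, the paired t-test has 30 independent differences. Simulated type I error (40,000 runs) is 4.8% to 5.0% for the right eye alone and 5.0% to 5.1% for the two-eye mean, at every ρ. The choice affects precision only. The SE of one eye relative to that of the mean is √(2/(1+ρ)); at ρ = 0.5 this is √(2/1.5) = 1.155, or 15% wider.

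**Step 2. Choosing after seeing the data.** The significant results from right eye, left eye and mean are counted in two ways: in either direction, and in favour of the coated lens only. The second matches the directional hypothesis in Specific Aims and has a nominal rate of 2.5%.

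**Step 3. Eyes as rows.** With 60 rows the true variance of the overall mean is (1+ρ) times the variance the test assumes. The large-sample error is therefore 2[1 − Φ(1.96/√(1+ρ))]. At ρ = 0.5 this is 2[1 − Φ(1.96/1.225)] = 2[1 − Φ(1.600)] = 11.0%, close to the simulated 11.2%. The effective number of observations is 60/(1+ρ), which is 40 at ρ = 0.5.

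| ρ | One-eye SE ÷ SE of mean | Any of three significant, either direction | Any of three significant, benefit only (nominal 2.5%) | 60 eyes as independent pairs |
|---|---|---|---|---|
| 0 | 1.414 | 11.7% | 6.0% | 5.1% |
| 0.3 | 1.240 | 10.6% | 5.4% | 8.6% |
| 0.5 | 1.155 | 9.8% | 5.0% | 11.2% |
| 0.7 | 1.085 | 8.6% | 4.4% | 13.5% |
| 0.8 | 1.054 | 8.0% | 4.0% | 14.7% |

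The benefit-only column comes from a separate run of 20,000; the other simulated columns are from 40,000. The signed-rank test behaves similarly: 11.7%, 10.9%, 10.0%, 9.0% and 8.1% for any of three in either direction.

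**Step 4. Does the plan lead to either bad case?** No section proposes trying several eyes and selecting, or entering eyes as rows. Specific Aims compares signs of subjects, which leans towards one value per participant. The study is double-masked, and an eye rule settled before the code is broken produces no inflation.

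**Step 5. Would settling the rule secure the sign family?** With one fixed value per sign and five tests at 5%, taken as independent for illustration, the chance of at least one false positive is 1 − 0.95⁵ = 22.6%. The signs remain supportive evidence whichever eye rule is used.

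**The case for a change.** The strongest case for a change is that the omission is real, nothing elsewhere repairs it, and one sentence would close it. Aim 2 is worded as a significance claim. A reader cannot tell from the plan whether a sign test will have 30 or 60 pairs. The inflation is not trivial if things go wrong: about 1.6 to 2.3 times nominal for a post hoc choice, and about three times for pooled eyes at ρ = 0.8.

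The omission stands, and so does the arithmetic as a conditional statement. Three things weaken the inference that the plan must change.

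- Right eye, left eye and mean all use the participant as the unit, and each is valid. What is open among them is a summary, and writing one down records a choice without correcting a method.
- The inflation belongs to selection or pooling that no section describes.
- A required two-eye average would assume that both eyes are recorded, which the documents do not say. It may also not suit staining, lid wiper epitheliopathy or papillary conjunctivitis if these are graded on ordinal scales, which the documents do not state either.

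The missing eye for the tear break-up entry criterion is an eligibility matter. An analysis rule would not settle it.

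**Conclusion.** No change to the plan follows. The Statistical Analysis section leaves out a detail that a competent analyst supplies as a matter of course: one value per participant for each sign, settled before unmasking. Any such rule holds the per-sign error at about 5%; the choice of eye or mean moves the SE by between 5% (ρ = 0.8) and 41% (ρ = 0).

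The adverse figures are about 8% to 12% for selection in either direction, 4% to 6% against 2.5% for false claims of benefit, and 5% to 15% for pooled eyes. They rest on the assumed 5% level, normal differences, equal variances and ρ from 0 to 0.8, and on conduct the plan does not propose. The exposure is confined to secondary signs, and the primary symptom outcomes are unaffected.

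### The planned paired t-test or signed-rank test ignores period in a two-period crossover: it loses power at 15/15 if scores shift between periods, and is biased if completers differ by sequence

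*Combined protocol and SAP*

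**What the plan says.** Experimental Design sets up two randomised sequences of equal size. For one of them, "Half of the participants (15) will be randomly chosen to wear the Hydra-Peg treated scleral lenses first for 30 days"; the remaining 15 take the two lens types in the opposite order. General Study Schedule puts the two outcome visits at Day 40 and Day 79.

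Statistical Analysis is the whole analysis plan. The quantity analysed is the treated-versus-untreated difference. After a normality check, "Normal distributions will be analyzed using a paired t-test"; where normality fails, the plan is that "Non-normal distributions will be analyzed with the Wilcoxon Signed Ranked test". Period, sequence, dropout and unequal completers are not mentioned there or elsewhere.

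Participant Recruitment states that "30 scleral lens wearers with CLD and moderate to severe DE shall be recruited", and Experimental Design that "30 subjects with symptomatic moderate to severe dry eye and symptoms of CLD will complete a double-masked cross-over study". The number recruited and the number completing are therefore the same, with no allowance for loss.

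Some features limit a shift between periods. Participants are established wearers who keep their supportive therapy outside the wash-outs and "use hydrogen peroxide for lens care throughout the study". In addition, "One week wash-out periods with no lens wear will be placed before and between the 30-day test periods", and testing hours are fixed.

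**The concern.** In a crossover, the treated and untreated measurements on one person are also a period 1 and a period 2 measurement. Both planned tests treat all 30 differences as one sample, although the two sequences have different expected differences whenever scores drift between periods. The randomised order, which would separate drift from treatment effect, is recorded but not used.

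The main stake is power: a 30-person trial could miss a real difference because removable variation is left in the error term. The second stake is the estimate itself. If one sequence loses more participants than the other, the primary contrast absorbs part of the drift, and the direction cannot be predicted.

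**Working it through.** **Inputs from the documents.** Two sequences of 15; outcomes at Day 40 and Day 79, 39 days apart; paired t-test or signed-rank test on the pooled differences.

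**Inputs assumed, because the documents give none.** Two-sided 5% level; SD of the within-person difference = 1, so all sizes are in SD units; true effect τ = 0.529, which gives 80% power for a paired t-test with n = 30 and no shift; period shift π from 0 to 1.0; various completer splits. The figure of 30 has no derivation, so it cannot be reproduced.

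**Algebra.** Let D be treated minus untreated, coded so that positive favours treated lenses, and π be period 2 minus period 1.

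- Treated-first: E(D) = τ − π
- Untreated-first: E(D) = τ + π
- Bias of the pooled mean = π × (n untreated-first − n treated-first) / N
- At 15/15 the bias is 0, but the expected sample variance is 1 + π² × 30/29. The standard error (SE) is therefore too large by √(1 + π² × 30/29).

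The adjusted analysis averages the two sequence means of D with equal weight. This gives [(τ − π) + (τ + π)]/2 = τ for any split. It uses the pooled within-sequence variance and N − 2 degrees of freedom.

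**Balanced completers, 15/15** (100,000 simulated trials per cell). The last column is 30/(1 + π² × 30/29), the number of people who would give the same SE with adjustment.

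| π | SE factor | Paired t type I error | Paired t power | Adjusted power | Equivalent N |
|---|---|---|---|---|---|
| 0 | 1.000 | 0.051 | 0.801 | about 0.80 | 30 |
| 0.25 | 1.032 | 0.044 | 0.781 | about 0.80 | 28.2 |
| 0.5 | 1.122 | 0.029 | 0.726 | about 0.80 | 23.8 |
| 1.0 | 1.426 | 0.006 | 0.499 | about 0.80 | 14.7 |

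Adjusted type I error was 0.050 to 0.051 throughout. A separate simulation of 20,000 trials per cell agreed with the paired t figures to within 0.01.

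**Rank tests, 15/15, normal data** (20,000 trials). At π = 0, 0.25, 0.5 and 1.0 the signed-rank test has type I error 0.048, 0.045, 0.028 and 0.005, and power 0.782, 0.764, 0.700 and 0.443. The rank-sum test on period differences keeps type I error at 0.049 to 0.051 and power at 0.778 to 0.780.

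**Unequal completers, π = 0.5** (treated-first/untreated-first):

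| Split | Bias | Paired t power | Adjusted power |
|---|---|---|---|
| 15/13 | 0.5 × (−2)/28 = −0.036 | 0.625 | 0.768 |
| 13/15 | +0.036 | 0.751 | 0.767 |
| 15/10 | 0.5 × (−5)/25 = −0.10 | 0.448 | 0.701 |
| 10/15 | +0.10 | 0.793 | 0.700 |

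The apparent gain at 10/15 is bias towards treatment. With π negative, the rows of each pair swap. Type I error clearly exceeds 5% only under heavy imbalance: at 15/8 it is 0.057, 0.072 and 0.093 for π = 0.25, 0.5 and 1.0. At 15/11 and π = 0.5 it is 0.041.

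**Random loss.** Losing two at random keeps exact balance with probability 15 × 15/435 = 0.52. Power is then 0.751 against 0.769 adjusted at π = 0.25, and 0.690 against 0.769 at π = 0.5. Losing five gives 0.695 against 0.714 and 0.630 against 0.714. At π = 0.5 and loss of five, mean bias is 0 and mean absolute bias 0.035.

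**The case against.** The planned test is valid for the planned design. At 15/15 the estimate is unbiased, type I error is at or below 5%, and adjustment returns the same point estimate. Only the standard error changes.

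Serious loss needs a shift of about 0.5 SD, nearly as large as the assumed treatment effect, and the documents do not point to one. If entry is staggered across three sites, season adds mostly between-person noise that a period term would not remove. The questionnaires have already been given on Day 1 and Day 9, so early practice effects should largely precede the Day 40 and Day 79 comparison. Power is also sensitive because the effect was set at 80%: at 15/15 and π = 0.5, an effect of 0.7 SD gives 93% against 96% adjusted, and 0.8 SD gives 98% against 99%. The extreme splits are rare under random loss: 15/10 or 10/15 has probability 4.2% after losing five, and 15/8 or 8/15 has 0.6% after losing seven.

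All of this is correct, and it limits the size of the problem. It does not remove it. The documents state no enrolment window, so a seasonal shift cannot be ruled out, nor can a further effect of repeating the questionnaires. Any odd number of completers is unbalanced by definition. The shift cannot be known beforehand, and an adjustment chosen after seeing the data would be open to criticism.

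**Conclusion.** The concern holds. The plan randomises order and then does not use it. That the test is conservative at 15/15 when scores shift between periods, and biased when completers are also unequal, follows from algebra. How large either effect is depends wholly on assumed values.

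The loss at 15/15 is about 2 power points for a 0.25 SD shift, 7 for 0.5 SD and 30 for 1.0 SD, and less if the true effect is well above 0.529 SD. Bias needs both a shift and unequal completers, and averages to zero if dropout is unrelated to sequence. The trial is not invalidated, but this should be fixed because the remedy is nearly free. Carry-over is a separate matter that this change does not address.

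**What to change.** In Statistical Analysis, replace the paired t-test with one prespecified primary analysis: a linear mixed model with fixed treatment, period and sequence and random participant, fitted by REML with Kenward-Roger degrees of freedom. Report the treatment difference with its 95% CI, and keep participants who have only one period. With complete data this is the two-sample t-test comparing period 1 minus period 2 differences between sequences. Half the between-sequence difference is the treatment effect, on 28 degrees of freedom at 30 completers.

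For non-normal or ordinal outcomes, replace the signed-rank test with the Wilcoxon rank-sum test on the same period differences between sequences, in participants with both periods. State in advance which route applies to OSDI and to CLDEQ-8.

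**Cost.** A few lines of text, no new data, and one degree of freedom (critical t 2.048 instead of 2.045 at 30 completers). With no period shift, the power cost is about 0.1 point at 15/15, 0.5 point on average after random loss of five, 2 points at 15/10 (72% to 70%) and about 4 points at 15/8.

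Keeping one-period participants adds little. With five untreated-first participants missing period 2 and within-person correlation of 0.3, 0.5 or 0.7, the SD of the estimate was 0.205, 0.195 and 0.200, against 0.208, 0.199 and 0.200 without them. That check used only 150 trials per correlation and did not assess type I error or power.
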